### 9.2.3 Biopsy Risks

Skin Biopsy - There will be temporary discomfort when the local anesthetic is injected and when its effect wears off. Some slight bleeding may occur after the biopsy. There is a rare risk of infection. The biopsy may leave a small scar. The scar may be permanent.

### 9.3 Mitigation of Risks

These risks are mitigated by utilizing qualified clinical investigators who have training and are experienced in (1) performing energy based and laser procedures and (2) following study treatment procedures. In addition, risks are mitigated by including only those subjects that meet the study eligibility criteria. The study also includes evaluation of study subject satisfaction with this procedure. Given the anticipated acceptable risk, the risk benefit assessment of the use of the CLEAR + BRILLIANT TOUCH® diode laser device to improve the appearance of photoaged skin appears to offer a substantial clinical benefit at a reasonable risk.

Further discussion of risks of the of the CLEAR + BRILLIANT TOUCH® System can also be found and should be accessed in the CLEAR + BRILLIANT TOUCH® Laser System User Manual provided by the Sponsor.

#### 10. STATISTICS

### 10.1 Statistical Analysis Populations and Demographics

The intent-to-treat (ITT) population will be the primary population for all statistical analyses. The ITT population will include all subjects who received treatment, participated in at least 1 post-baseline evaluation, and were not otherwise disqualified.

Subjects may be removed from the analysis in the case of an AE, SAE, noncompliance, or Investigator decision. The reason for any subject(s) excluded from an analysis population will be documented in a note to file and included in the study report.

Demographic data and baseline characteristics, including age, gender, ethnicity, Fitzpatrick skin type, Glogau rating, and Fitzpatrick wrinkle & elastosis scale rating, will be summarized according to the analysis population for all subjects. For continuous variables, descriptive statistics including number of subjects (N), mean, median, standard deviation (SD), minimum (MIN) and maximum (MAX) values will be presented. For categorical variables, the count and percentage of each category will be provided. The denominator for all percentages will be the number of subjects with non-missing data at the given visit for each respective study treatment, unless otherwise indicated.

The sample size determination of this study is based on the Sponsor's recommendations to quantify the effectiveness and safety of the CLEAR + BRILLIANT TOUCH® diode laser 1440-nm and 1927-nm Laser in the context of this study. Power calculations were performed based on estimates for expected mean change and variance in overall appearance at 3 months as rated by the Investigator using the Quartile Improvement Scale from study 12-133-CBP-F ('Evaluation of the skin after treatment with the Clear + Brilliant 1927-nm wavelength laser by means of the VISIA-CA Imaging System'). The power calculations demonstrated a sample size of 25 has greater than 95% power to reject the null hypothesis (change from baseline=0) for the primary efficacy endpoint. Thus, up to 30 subjects will be enrolled to account for potential drop-out.

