### 4.2.3 Safety Endpoints

Serious Adverse Events (SAEs) related and unrelated to the treatment procedure or to the CLEAR + BRILLIANT TOUCH® diode laser.

The severity of post-treatment skin responses:

- Immediate post-treatment erythema and edema (Visits: 1 and or 2 if screening and treatment on same day, Visits 3, 4 and 5)
- Prolonged post-treatment erythema, edema, dryness/flakiness, hypopigmentation, hyperpigmentation, blistering, scarring. (Visits 6 & 7)

The evaluation of pain and discomfort immediately after the treatment (within 60 minutes) as reported by the subject on a visual analog scale (VAS).

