#### 7.2 Investigator Evaluations Quartile Improvement Score

Treating Investigators will compare:

- 1. Baseline photographs to one-month post treatment.
- 2. Baseline photographs to three-months post treatment.

A Quartile Improvement Scale will be used to individually score each category: (a) fine wrinkles, (b) skin texture, (c) dyschromia/pigment, (d) skin radiance, (e) pore size and (f) overall appearance.

Investigator Quartile Improvement Score				
Rating	Percentage (%)	Score		
No Improvement	0%	0		
Minor/Mild Improvement	1%-25%	1		
Moderate Improvement	26%-50%	2		
Marked Improvement	51%-75%	3		
Very Significant Improvement	76%-100%	4		

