### 8.2 Adverse Event / Device Malfunction Reporting

In the case of an AE (Serious and Significant Non-Serious) or UADE the Investigator must:

Report the AE or UADE to the Medical Monitor within 24 hours of knowledge of the event using the Sponsor-provided form (SAE/UADE reporting form, Appendix D) by emailing the completed form to the Medical Monitor

The Medical Monitor will email/fax a copy of the form immediately (within 24 hours) for SAEs/UADEs only to upon receipt.

In the case of Device Malfunctions, the Investigator must:

Report the Device Malfunction within 24 hours using the Sponsor-provided form (Device Malfunction reporting form, Appendix E) by emailing the completed form to

All AEs observed by study subjects, Investigators or other study staff from first exposure to the study product through last study follow-up visit will be recorded. If a device-related AE, SAE, unanticipated serious device related effect or device malfunction is ongoing at the final study visit, the subject will be followed until resolution, until the condition stabilizes, until the event is otherwise explained, or the subject is lost to follow-up. The Investigator should make every effort to ensure the follow-up includes any supplemental investigations as may be indicated to elucidate, as completely practical, the nature and or causality of the AE or SAE. This may include unscheduled follow up visits for AE assessment.

Study subjects will be instructed to report all adverse events to the clinical study staff and information will be collected throughout the study and recorded on the case report forms and reported to Solta Medical Customer Service.

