### 10.2 Statistical Analysis Plan (SAP)

#### 10.2.1 Descriptive Statistical Summary

A descriptive statistical summary will be provided for Investigator Quartile Improvement Score (IQIS, 0-4), tolerability parameters, VAS scores, and biopsy parameters. The descriptive statistical summary includes the N, mean, median, SD, MIN, and MAX of scores/values at all applicable time points.

Counts and percentages will be provided for Investigator Quartile Improvement Score (rating), SAE parameters, tolerability parameters, VAS (in category), and individual response data (GAIS and subject satisfaction).

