#### **Statistical Analysis Plan Table**

Evaluation	Change from baseline	Notes/Interpretation
Investigator	The mean score (0-4) will	Significantly greater than 0
Quartile	be compared to the	indicates improvement.
Improvement	constant 0, using Wilcoxon	
Score	signed rank test	
SAEs	NA	Zero or low number of SAEs is
		favorable
Tolerability	NA	Lower score indicates better
parameters		tolerability
VAS	NA	Lower score indicates better
		tolerability
Biopsy parameters	NA	Descriptive statistics only
Individual	NA	A binomial test (sign test) P value
response data		will be provided. A higher
(GAIS and		percentage of combined favorable
satisfaction)		responses with a significant P
		value indicates positive subject
		perceptions of the test material.
Blinded	The mean score (0-4) will	Significantly greater than 0 indicates
Investigators	be compared to the	improvement.
	constant 0, using Wilcoxson	
	signed rank test	

All statistical tests will be 2-sided at significance level alpha=0.05 unless specified otherwise. *P* values will be reported to 3 decimal places (0.000).

No multiple testing corrections will be considered in the study. Statistical analyses are performed using SAS software version 9.4 (SAS Statistical Institute). The statistical results will be sent to the Sponsor along with raw data in a Microsoft Excel document at completion of the study.

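### Section 10.1 allows a subject to be dropped from analysis because of an AE or SAE and defines no safety population, so the safety summaries can omit the subjects who had the events

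*Combined protocol and SAP*

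**What the plan says.** Section 10.1 sets one analysis population: "The intent-to-treat (ITT) population will be the primary population for all statistical analyses". Membership requires that a subject was treated, "participated in at least 1 post-baseline evaluation, and were not otherwise disqualified". Disqualification is not defined. The section then adds: "Subjects may be removed from the analysis in the case of an AE, SAE, noncompliance, or Investigator decision". The reason for each exclusion must be filed and given in the study report.

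The safety endpoints in section 4.2.3 begin with "Serious Adverse Events (SAEs) related and unrelated to the treatment procedure" or the device, followed by skin-response severity and VAS pain. Section 10.2.1 plans the outputs: "Counts and percentages will be provided for Investigator Quartile Improvement Score (rating), SAE parameters, tolerability parameters", and VAS by category; tolerability and VAS scores are also summarised descriptively. In the Statistical Analysis Plan Table, the interpretation note for SAEs opens "Zero or low number of SAEs is" and goes on to call that result favourable. No part of section 10 names a different population for these outputs.

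On collection, section 8.2 says that all observed AEs "from first exposure to the study product through last study follow-up visit will be recorded". On effectiveness, section 7.2 assigns the primary scoring to the site: "Treating Investigators will compare" the baseline photographs with those at one and three months.

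**The concern.** The event being counted is itself a listed ground for leaving the subject out of the count. Safety is half of the study objective in section 3. In an uncontrolled study of at most 30 subjects, one removal can decide whether the SAE table reads zero. The requirement of at least one post-baseline evaluation adds a smaller risk, because a subject who leaves early after an event might not meet it.

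A second, lesser point concerns effectiveness. Removal by investigator decision has no criteria and no stated timing, and the treating investigators score the primary endpoint with knowledge of which photograph is which. Exclusions could therefore depend on outcome, although the plan does not say that they will.

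**Working it through.** **Plan's own figure.** The only quantitative statement in section 10.1 is that 25 subjects give more than 95% power, with up to 30 enrolled to cover drop-out. The mean change and SD behind it are not given, so it cannot be reproduced. Solving backwards with a one-sample t test at two-sided 0.05, 95% power with n = 25 needs a mean/SD of about 0.75. The present point does not depend on that figure; 25 and 30 are used below only as study sizes.

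**Safety.** The numbers of subjects with an SAE are assumptions. The exact (Clopper-Pearson) 95% limits for x events in n subjects are the 2.5% quantile of Beta(x, n − x + 1) and the 97.5% quantile of Beta(x + 1, n − x). For x = 0 the lower limit is 0 and the upper limit is 1 − 0.025^(1/n); for n = 29 this is 1 − 0.025^(1/29) = 11.9%.

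| Treated | With an SAE (assumed) | All treated: % (95% CI) | After permitted removal: % (95% CI) |
|---|---|---|---|
| 30 | 1 | 1/30 = 3.3 (0.1 to 17.2) | 0/29 = 0 (0 to 11.9) |
| 30 | 2 | 2/30 = 6.7 (0.8 to 22.1) | 0/28 = 0 (0 to 12.3) |
| 30 | 3 | 3/30 = 10.0 (2.1 to 26.5) | 0/27 = 0 (0 to 12.8) |
| 25 | 1 | 1/25 = 4.0 (0.1 to 20.4) | 0/24 = 0 (0 to 14.2) |
| 25 | 3 | 3/25 = 12.0 (2.5 to 31.2) | 0/22 = 0 (0 to 15.4) |

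Both the estimate and the upper limit fall in every row.

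**VAS.** Suppose 27 subjects score 3 and three subjects score 8, and those three are removed after an AE. The mean falls from (27 × 3 + 3 × 8)/30 = 105/30 = 3.5 to 3.0, and the maximum from 8 to 3.

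**Primary effectiveness score (IQIS, 0 to 4).** Removing k zero scores from 30 leaves the sum unchanged, so the mean is multiplied by 30/(30 − k). For k = 1, 3 and 5 this is 30/29 = 1.034, 30/27 = 1.111 and 30/25 = 1.200, that is, rises of 3.4%, 11.1% and 20%.

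The signed rank test behaves differently, because in its standard form it drops zeros. Take 18 positive scores (nine 1s, six 2s, three 3s; sum 9 + 12 + 9 = 30). With 12, 7 or 0 zeros the mean is 30/30 = 1.00, 30/25 = 1.20 or 30/18 = 1.67. The p-value by normal approximation is 0.00015 each time.

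**GAIS and satisfaction (exploratory).** Exact two-sided binomial test against 0.5, counting every non-favourable answer as unfavourable: 20 of 30 gives p = 0.099. With two unfavourable responses removed, 20 of 28 gives p = 0.036.

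**The case against.** The rule is permissive. A wrong rate arises only if a subject is removed and the removal is carried into the safety tables, and the plan requires neither. Calling the ITT set primary also leaves room for another set. Concealment is limited: SAEs go to the sponsor within 24 hours (section 8.1.1), AEs are recorded (section 8.2), and the study report must give the reason for each exclusion, so a careful reader could restore the count. The device is cleared, and section 9.2.1 expects very few complications. If no SAE occurs, the SAE table is unaffected, and rates of 10% or 12% are pessimistic illustrations.

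These points bear on how likely and how visible the problem is. They do not remove it. The recording and reporting rules govern collection; none of them puts a removed subject back into the numerator and denominator. No other population is defined. Removal for a non-serious AE would still distort the tolerability and VAS summaries with no SAE at all.

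The effectiveness part is properly secondary. The primary p-value does not move when zeros are removed. The binomial example is also a favourable case: with two unfavourable responses removed from 30, 20 is the only favourable count from 18 to 22 at which the result crosses 0.05 (19 goes from 0.200 to 0.087; 21 is already at 0.043). Section 10.2.2 also does not say whether neutral answers count as unfavourable.

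**Conclusion.** The concern holds and should be corrected before any analysis. A stated rule, not merely a missing detail, permits the SAE, tolerability and VAS summaries to leave out subjects because of the events being summarised. On assumed counts of one to three subjects with an SAE among 30 treated, a true 3.3% to 10.0% would be reported as 0%, and the upper confidence limit would fall from 17.2–26.5% to 11.9–12.8%. These sizes depend on the assumed counts and on the discretion being used.

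For effectiveness, the descriptive mean and the percent improved can be raised and an exploratory binomial result can change. The primary signed rank test is not affected by removing zero scores.

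**What to change.** - In section 10.1, delete the sentence that permits removal, and delete the closing condition on disqualification from the ITT definition.
- Define a safety population of every subject who received any study treatment, with no removals. Use it for all SAE, AE, skin-response, diary and VAS summaries. Section 5.6 already counts a subject as enrolled at the first treatment, so this set needs no new data.
- Define the primary effectiveness population as all treated subjects with at least one post-baseline effectiveness evaluation, with no removal for an AE, SAE, noncompliance or investigator decision. The mean IQIS and the signed rank test use the observed scores at the visit.
- That set omits subjects who leave before the first scoring at Visit 6. Add a sensitivity row giving the percent improved on the primary endpoint at 3 months among all treated subjects, with missing counted as not improved.
- Confine noncompliance exclusions to a supportive per-protocol analysis, with criteria written down before the first Visit 6 scoring. The site will already have seen subjects at the treatment visits, so this limits outcome-dependent exclusion but does not rule it out; the analysis should stay supportive.

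The first two changes cure the safety defect. The cost is revised wording in section 10.1, one sensitivity row and one supportive table, with no added visits, subjects or procedures. The downside is that reported rates may be less favourable when subjects have events or drop out.

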#### 5.9.1 Reason for Withdrawal or Termination

A study subject will be discontinued from participation in the study if:

- Any clinical adverse event (AE), laboratory abnormality, intercurrent illness, or other medical condition or situation occurs such that continued participation in the study would not be in the best interest of the subject.
- The subject meets any exclusion criteria (either newly developed or not previously recognized).

Subjects who are withdrawn will not be replaced.

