#### 5.9.2 Handling of Subject Withdrawal or Termination

If a subject voluntarily withdrawals, they will not be asked to continue the scheduled evaluations due to the short study duration. If subject is withdrawn from study because of adverse events they will be provided with the appropriate care under medical supervision.

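### The 3-month percentages labelled ITT are observed-case figures, and no analysis of the missing subjects is planned beside them

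*Combined protocol and SAP*

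**What the plan says.** Section 10.1 names ITT as the primary population for all analyses. Membership requires that subjects were treated, "participated in at least 1 post-baseline evaluation, and were not otherwise disqualified". The same section then fixes the denominator: "The denominator for all percentages will be the number of subjects with non-missing data at the given visit", followed by "for each respective study treatment, unless otherwise indicated". Nothing in Sections 10.1 to 10.2.3 indicates another denominator for IQIS, GAIS or satisfaction. Those sections also contain no imputation, non-responder rule or missing-data sensitivity analysis.

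On departures, Section 5.9.1 states: "Subjects who are withdrawn will not be replaced". After voluntary withdrawal, Section 5.9.2 says of subjects that "they will not be asked to continue the scheduled evaluations due to the short study duration". For the other case it says: "If subject is withdrawn from study because of adverse events they will be provided with the appropriate care under medical supervision". It is silent on whether those subjects still receive the 3-month ratings. Section 5.9 ends all data collection when consent for future disclosure is also withdrawn. Under Section 5.8, subjects who miss visits or measurements stay in the study.

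In the Schedule of Events (6.8), IQIS is rated only at Visits 6 and 7, and GAIS and satisfaction only at Visit 7. Section 10.2.1 commits to counts and percentages for all three. Section 10.2.2 tests mean IQIS against 0 (the SAP table names the Wilcoxon signed rank test) and applies a binomial sign test to GAIS and satisfaction.

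**The concern.** A reader who sees ITT expects the result to speak for everyone treated. Here a subject can enter the population through any post-baseline evaluation, such as side-effect scoring at Visit 3, leave during the treatment series, and contribute to none of the 3-month percentages. The label and the denominator then describe different groups.

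The loss may also be related to outcome. There is no control group, and subjects and treating investigators know what was given. Section 5.9.1 discontinues a subject for an adverse event that makes continuing unwise, or for a newly developed exclusion criterion; the exclusion list in 5.4 includes rashes, burns, inflammation and open wounds. Subjects who react badly, or who see no benefit, could therefore be over-represented among the missing. What is at stake is the reported improvement, GAIS and satisfaction percentages, and whether the two subject-reported tests are significant.

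**Working it through.** **1. Inputs.** From Section 10.1: n = 25 for more than 95% power, and up to 30 enrolled to allow for drop-out. From Section 10.2: two-sided alpha 0.05, exact binomial sign test, Wilcoxon signed rank test. Under Section 5.6 enrollment occurs at the first treatment, so 30 enrolled means 30 treated. The response counts below are illustrative.

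**2. The plan's own figures.** The power statement cannot be reproduced because the mean and SD from the earlier study are not given. At n = 25, 95% power needs a standardized effect of about 0.75 (two-sided one-sample t), or about 0.79 with the sample size scaled by 0.955 to approximate the Wilcoxon test. No drop-out rate is stated. Working back, 25/(1 − d) = 30 gives d = 5/30 = 16.7%. A rate of 15% also rounds up to 30 (25/0.85 = 29.4), and 20% would need 32 (25/0.80 = 31.25). Five missing is therefore an assumption consistent with the plan.

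**3. Percentages.** With r improved among m observed and M missing, N = m + M. The plan reports r/m. The all-treated figure lies between r/N (no missing subject improved) and (r + M)/N (all improved).

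| Missing M | Reported r/m | All-treated range |
|---|---|---|
| 0 | 24/30 = 80.0% | 80.0% |
| 1 | 23/29 = 79.3% | 76.7% to 80.0% |
| 3 | 22/27 = 81.5% | 73.3% to 83.3% |
| 5 | 15/25 = 60.0% | 50.0% to 66.7% |
| 5 | 20/25 = 80.0% | 66.7% to 83.3% |
| 5 | 22/25 = 88.0% | 73.3% to 90.0% |

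The largest overstatement is r/m − r/N = (r/m) × (M/N). With M = 5 and N = 30 it is at most 16.7 points; at 80% observed it is 0.80 × 5/30 = 13.3 points. The largest understatement at 80% is 83.3 − 80.0 = 3.3 points. Break-even is 4 of the 5 missing improved: (20 + 4)/30 = 80%. The exact 95% interval is 59% to 93% for 20/25 and 47% to 83% for 20/30.

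**4. Sign tests.** p = min(1, 2 × P(X ≥ r)), X binomial(n, 0.5). This assumes that every rated subject is classed as favorable or unfavorable, and that missing counts as not favorable.

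| Favorable | n = 25 observed | n = 30 all treated |
|---|---|---|
| 18 | p = 0.043 | p = 0.36 |
| 19 | p = 0.015 | p = 0.20 |
| 20 | p = 0.004 | p = 0.099 |
| 21 | p = 0.0009 | p = 0.043 |

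The conclusion changes for 18 to 20 favorable of 25 (72% to 80%). From 21 upwards it does not.

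**5. Primary test and mean.** IQIS runs from 0 to 4 and cannot be negative. If the signed rank test discards zeros, adding five subjects scored 0 adds nothing to the statistic and the p-value is unchanged; any 6 positive scores with no negatives already give 2 × 0.5^6 = 0.031. The mean does move: 2.0 in 25 becomes 2.0 × 25/30 = 1.67 in 30.

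**The case against.** The best defence is that the specified primary analysis is a test of the score, not a proportion, and step 5 shows it is probably unaffected. No responder threshold is set, so no pass/fail decision rests on a percentage. GAIS and satisfaction are exploratory. That defence stands, and it confines the point to the reported percentages, the mean and the two sign tests.

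The plan also limits and documents losses. Subjects with missed visits stay in, efforts are made to reach those lost to follow-up (5.9), ongoing device-related events are followed (8.2), N is shown for IQIS at each time point (10.2.1), and withdrawal reasons go on the exit form. This helps transparency, but none of it puts missing subjects back into a percentage or a test.

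A reader might infer several stronger things that the documents do not support:

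- That the figures are biased upward. Direction depends on how the missing subjects fared, and step 3 allows a small understatement too.
- That no withdrawn subject is assessed. The text says so only for voluntary withdrawal and withdrawn consent; for adverse-event withdrawals it is silent on effectiveness ratings.
- That the result is strictly a completer analysis. A subject who missed earlier visits but attends Visit 7 is counted.
- That the denominator rule is absolute. It is a default that permits exceptions, though none is given for these outcomes.
- That counting missing as failure should replace the headline. That is a worst-case assumption, and making it the sole headline is a matter of preference.

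Section 10.1 also states: "Subjects may be removed from the analysis in the case of an AE, SAE, noncompliance, or Investigator decision". That is a separate route of selection, since it can take out subjects who do have 3-month data.

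**Conclusion.** The point holds in a conditional form. The 3-month IQIS, GAIS and satisfaction percentages are observed-case figures presented under an ITT label, with nothing planned to show how much the missing subjects could matter. If 5 of 30 are missing, the reported percentage can exceed the all-treated one by up to 16.7 points, and a GAIS or satisfaction result between 18/25 and 20/25 favorable would lose significance when missing counts as not favorable. With nobody missing there is no difference.

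This rests on an inferred loss of 5, illustrative response counts, and a missing group that did worse than those seen, which is plausible but not shown. The primary p-value is not called into question if zeros are discarded; since zero handling is unspecified, that too is an assumption.

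**What to change.** In Section 10.1, add that the 3-month IQIS, GAIS and satisfaction percentages, and the GAIS and satisfaction sign tests, will also be reported on all subjects who received at least one treatment, with a missing rating counted as not improved or not favorable. Place these beside the figures on non-missing data, label the latter observed-case, and give the number of missing 3-month ratings with reasons.

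The cost is a sentence or two and one extra table, with no added visits or subjects. The downside is that a lower percentage may appear next to the headline.
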